7.2 Medical History

Medical history data will be summarized and presented using body systems and conditions/diagnoses as captured on the eCRF. The body systems will be presented in alphabetical order and the conditions/diagnoses will be presented in alphabetical order within each body system. The number and percentage of subjects with a particular condition/diagnosis will be summarized. Subjects reporting more than one condition/diagnosis within a body system will be counted only once for that body system.

7.3 Previous Treatment and Concomitant Medications

Prior and concomitant medications will be summarized. A prior medication is defined as any medication taken prior to the date of the first dose of study drug. A concomitant medication is defined as any medication that started prior to the date of the first dose of study drug and continued to be taken after the first dose of study drug or any medication that started on or after the date of the first dose of study drug, but not after the date of the last (maximum) dose of study drug. Concomitant medications will be summarized for all subjects in the Safety population. The number and percentage of subjects taking prior or concomitant medications will be summarized by generic drug name based on the WHO Drug Dictionary. Note that prior HCV medications (IFN, pegIFN and RBV) will be summarized separately from other prior medications.

Medications for the treatment of HCV will be collected in the PT Period and will be summarized by generic drug name. A post-treatment medication for the treatment of HCV is defined as any medication taken on or after the last dose of study drug and entered as "Post treatment HCV medications" on the eCRF.

8.0 Patient Disposition

The number of subjects for each of the following categories will be summarized overall and by each investigator on the safety population.

- Subjects who took at least one dose of study drug;
- Subjects who completed study drug;
- Subjects who discontinued from study drug;
- Subjects who completed the study;
- Subjects ongoing in the Post-Treatment Period at the time of the interim analysis;
- Subjects who discontinued from the study.

The number and percentage of subjects who discontinued study drug will be summarized by reason (all reasons) and by primary reason (per eCRF). Similar summaries will be provided for discontinuations from the study.

The number and percentage of subjects will be summarized for:

- Subjects with interruptions of all study drugs for toxicity management;
- Subjects with any RBV dose modification;
 - Subjects with RBV dose modification due to decrease in hemoglobin;
 - Subjects with RBV dose modification due to decrease in creatinine clearance;
 - Subjects with RBV dose modification due to weight change;
 - Subjects with RBV dose modification due to other reasons;
- Subjects with any RBV dose modification to 0 mg (i.e., RBV interruptions).

Reasons for study drug interruptions and RBV dose modifications will be presented in the CSR listings.

9.0 Study Drug Exposure and Compliance

9.1 Exposure

The duration of exposure to study drug will be summarized for the safety population. Duration of exposure is defined for each subject as the last study drug dose date minus the first study drug dose date plus 1 day.

Descriptive statistics (n, mean, SD, median, minimum, and maximum) will be presented. Study drug duration also will be summarized with frequencies and percentages using the following categories depending on the treatment duration:

- 12 weeks of treatment: 1 to 15 days, 16 to 30 days, 31 to 45 days, 46 to 60 days, 61 to 76 days, and > 76 days.
- 24 weeks of treatment: 1 to 15 days, 16 to 30 days, 31 to 60 days, 61 to 90 days, 91 to 120 days, 121 to 153 days, and > 153 days.

9.2 Compliance

At each protocol-specified visit, the total number of tablets dispensed and returned is recorded together for ABT-450/r/ABT-267 and ABT-333, and is recorded separately for RBV. The compliance for ABT-450/r/ABT-267 and ABT-333 combined and the compliance for RBV within the Treatment Period will be calculated as the percentage of tablets taken (presumed as [tablets dispensed-tablets returned]) relative to the total capsules or tablets, respectively, expected to be taken. The total number of tablets prescribed will be equal to the total number of tablets that should have been taken per the protocol for the duration that the subject was in the Treatment Period (date of last dose – date of first dose + 1 day). Study drug interruptions due to an adverse event or other planned interruptions recorded on the eCRF will be subtracted from the duration. For compliance to RBV, RBV dose modifications due to adverse events, toxicity management, or weight changes as recorded on the RBV Dose Modifications eCRF will be used to modify the total number of tablets that should have been taken. A subject is considered to be compliant if the percentage is between 80% and 120%. Compliance will

be calculated for each subject and summarized with the n, mean, median, SD, minimum, and maximum. In addition, the percentage of compliant subjects will be calculated separately for ABT-450/r/ABT-267 + ABT-333, and RBV.

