5.5.2.1 Packaging and Labeling

ABT-450/r/ABT-267 and ABT-333 tablets will be supplied in weekly kits. Each kit will consist of a blister card containing 1 week of study medication plus one additional day of drug. There will be 16 ABT-333 250 mg tablets and 16 ABT-450/r/ABT-267 75 mg/50 mg/12.5 mg tablets for a total of 32 tablets per blister card.

The blister cards indicate which drugs on the card should be taken in the morning (both ABT-450/r/ABT-267 tablets and one ABT-333 tablet) with a picture of a sun and which should be taken in the evening (one ABT-333 tablet) with a picture of a moon.

Ribavirin tablets will be supplied to the site in bottles containing 168 tablets.

All study drugs will be labeled as required per country requirements.

The labels must remain affixed to the primary and potential secondary packaging material. All blank spaces should be completed by site staff prior to dispensing to subject.

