5.5.7 Drug Accountability

The investigator or his/her representative will verify that study drug supplies are received intact and in the correct amounts using the IRT system. A current (running) and accurate inventory of study drug will be kept by the investigator or his/her designated and qualified representatives and will include lot number, number of tablets dispensed, subject number, username of person who dispensed study drug and date dispensed for each subject. Final accountability will be verified by the monitor at the end of study drug treatment at the site.

During the study, should an enrolled subject misplace or damage a study drug kit, the IRT system must be contacted and informed of the misplaced or damaged study drug. If the kit is damaged, the subject will be requested to return the remaining study drug to the site. Replacement study drug may only be dispensed to the subject by contacting the IRT system. Study drug replacement(s) and an explanation of the reason for the misplaced or damaged study drug(s) will be documented within the subject source documentation.

Study drug start dates for each drug and the last dose of the regimen will be documented in the subject's source documents and recorded on the appropriate eCRF. The status of each kit, number of tablets remaining in each one returned, and the date of reconciliation will be documented in the IRT system at Study Visits defined as Study Drug Returned for IRT Reconciliation in [Table 7](#). The monitor will review study drug accountability on an ongoing basis.

Upon completion of or discontinuation from the Treatment Period, all original study drug bottles (containing unused study drugs) will be returned to the Sponsor (or designee) or destroyed on site. All destruction procedures will be according to instructions from the Sponsor and according to local regulations following completion of drug accountability

procedures. The number of tablets of each type of study drug returned in each kit will be noted in the IRT system. Labels must remain attached to the containers.

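### The adherence endpoint counts tablets in unreturned or lost kits as taken, so a full-course subject who returns no DAA cards scores about 114% and is classed compliant

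*SAP*

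**What the plan says.** SAP 9.2 defines adherence separately for the two DAA products combined and for ribavirin. In each case it is "calculated as the percentage of tablets taken (presumed as [tablets dispensed-tablets returned]) relative to the total capsules or tablets" expected. The expected number is what the protocol calls for "for the duration that the subject was in the Treatment Period (date of last dose – date of first dose + 1 day"). The section adds: "Study drug interruptions due to an adverse event or other planned interruptions recorded on the eCRF will be subtracted from the duration". It then sets a band: "A subject is considered to be compliant if the percentage is between 80% and 120" per cent. SAP 10.4 makes the percentage a secondary efficacy endpoint and refers to 9.2 for its calculation. The compliant/non-compliant split is a further summary in 9.2.

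On packaging, Protocol 5.5.2.1 says "Each kit will consist of a blister card containing 1 week of study medication plus one additional day of drug", "for a total of 32 tablets per blister card", and "Ribavirin tablets will be supplied to the site in bottles containing 168 tablets".

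Protocol 5.5.6 asks subjects to bring every kit to each visit, used or not, and asks sites to enter each kit's status, its exact remaining count and the reconciliation date in the IRT system. Protocol 5.5.7 foresees misplaced and damaged kits: "Replacement study drug may only be dispensed to the subject by contacting the IRT system". Neither document says how a kit that does not come back, or a kit that was lost and replaced, enters the calculation.

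**The concern.** Under a dispensed-minus-returned rule, every tablet that is not physically handed back is credited as swallowed. The band should show when the figure is implausible, but its upper tolerance (20%) is wider than the DAA overage (one extra day in seven, 14.3%). Over a full course, complete non-return therefore cannot push the DAA score past the upper limit.

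At stake is a stated secondary objective whose only measure is the pill count. The study also runs a care-plan programme meant to support adherence, so readers will take the reported figure at face value.

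**Working it through.** **Inputs.** DAA tablets per day: 2 + 1 in the morning and 1 in the evening = 4 (Protocol 5.5.4). Tablets per card: 32 (Protocol 5.5.2.1). Ribavirin: 168 per bottle (5.5.2.1), with 5 tablets a day at 1000 mg and 6 at 1200 mg (5.5.1). Dispensing is at Day 1 and Week 4, plus Week 12 for 24-week subjects (Protocol Table 7). The number of cards or bottles per visit is not stated. I assume one card per planned week and one bottle per four weeks.

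**Stated figure reproduced.** Eight days × 4 tablets = 32 per card, as the protocol says. Seven days need 28.

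**DAA, nothing returned.** Score = tablets dispensed / (4 × net treatment days).

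| Course | Net days | Score | Class |
|---|---|---|---|
| 12 weeks, 12 cards | 84 | 384/336 = 114.3% | compliant |
| 24 weeks, 24 cards | 168 | 768/672 = 114.3% | compliant |
| 12 weeks | 80 | 384/320 = 120.0% | on the limit |
| 24 weeks | 160 | 768/640 = 120.0% | on the limit |
| 12 weeks | 79 | 384/316 = 121.5% | not compliant |
| 12 weeks | 77 | 384/308 = 124.7% | not compliant |
| 12 weeks | 56 | 384/224 = 171.4% | not compliant |
| Stopped before the Week 4 supply, 4 cards | 28 | 128/112 = 114.3% | compliant |

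Actual intake does not enter the score. A subject who took only the first and last day's tablets of a 12-week course (8/336 = 2.4%) would also score 114.3%.

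**Returns needed to fall below 80%.** At 84 days, 0.8 × 336 = 268.8. At least 116 of the 384 tablets (30%) must be handed back, in any split between the two types. Of these, 384 − 336 = 48 are the routine overage.

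**One lost and replaced card, every dose taken, all unused tablets returned.** (336 + 32)/336 = 368/336 = 109.5%.

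**Effect on the mean.** If a share p of subjects are full-course non-returners with true intake t, the mean is too high by p × (114.3 − t) points. The documents give no value for p. With p = 10%, the excess is 1.4 points at t = 100 and 4.4 points at t = 70.

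**Ribavirin, nothing returned, three bottles for 12 weeks.** At 1200 mg, 504/(6 × 84) = 504/504 = 100%. At 1000 mg, 504/(5 × 84) = 504/420 = 120.0%, exactly on the limit; at 83 days it is 504/415 = 121.4%.

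**The case against.** The strongest reply is that the trial already controls this. Subjects are told to bring back all kits, sites count what remains and counsel poor adherers, and the monitor reviews accountability throughout and verifies it at the end of treatment (Protocol 5.5.6 and 5.5.7). The endpoint is descriptive, and the documents give no non-return rate. All of that stands and limits the importance of the point. It does not tell the analyst what to do when a kit is missing. After Week 4 the next scheduled visit is Week 12, so one missed return can leave eight weeks of cards uncounted.

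A second reply is that SAP 6.3 rules out imputation in efficacy analyses beyond listed exceptions, and adherence is not listed. Scoring an unrecorded return as zero is arguably an imputation. However, 9.2 states its own presumption explicitly, and the general line does not override it.

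Several stronger readings are tempting but unsupported:

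- A reader might infer that the extra day per card is what keeps a non-returner inside the band. Without it, the score would be 336/336 = 100%, also inside. The cause is the presumption itself.
- A reader might infer that every non-returner is classed compliant, so the percentage compliant can only be overstated. A fully adherent non-returner who stops at day 77 scores 124.7% and is classed non-compliant. That summary can err either way.
- A reader might infer that ribavirin repeats the DAA pattern. At 1200 mg there is no overage, and at 1000 mg the class depends on whether the limit is included.
- A reader might infer that a link between poor adherence and SVR12 failure is hidden. No such analysis is planned: adherence is not among the subgroups or logistic predictors in SAP 10.5. Nor do the documents show that poor adherers are less likely to return packs.

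**Conclusion.** The point holds in limited form. As written, SAP 9.2 credits unreturned and lost tablets as taken. This can only raise an individual subject's percentage, and so the mean.

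A DAA subject with at least 80 of 84, or 160 of 168, net treatment days who returns nothing scores between 114.3% and 120%. That subject is classed compliant; at exactly 120% this requires the limit to be included, which 9.2 does not settle. With fewer net days the score generally passes 120%, except for those who stop near the end of a dispensing interval. Subjects above the band still enter the mean uncapped.

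These figures rest on one card per planned week and one bottle per four weeks; further kits would raise the scores. How far the reported mean moves depends on a non-return rate that the documents do not give. This is a cheap improvement to a descriptive secondary endpoint and does not touch the primary analysis.

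**What to change.** Amend SAP 9.2 as follows.

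- Compute adherence from kits whose return and tablet count are recorded in IRT. Remove unreturned, lost or damaged kits from tablets taken, and remove from tablets expected the dosing days that those kits were to cover. Where a reconciled replacement covers the same days, count those days once, through the replacement. The fully adherent subject with one replaced card then scores 336/336 = 100%.
- Report the number of subjects without full reconciliation in a separate row.
- State whether 80% and 120% are inside the band.
- Add one sensitivity analysis that counts tablets in unreturned kits as not taken.

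Capping each subject at 100% is not a substitute, because a non-returner would still be classed compliant.

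The cost is SAP wording and minor programming. No new data are needed, since kit status, remaining tablets and reconciliation date are already in IRT. Adherence figures will be somewhat lower, and some subjects will contribute partial data. Tablets discarded before empty cards are returned remain undetectable by any pill count.

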10.0 Efficacy Analysis

10.1 General Considerations

The primary efficacy analysis on clinical outcomes will be performed on all subjects in the ITT population as defined in Section 5.1. All other efficacy analyses will be performed on the ITT-II population.

Treatment effects will be evaluated based on a two-sided significance level of 0.05 (when rounded to three decimal places). The data from the ITT-II population will be presented in one column/row as it represents the labelled treatment.

Plasma HCV RNA levels will be determined for each sample collected by the central laboratory using the COBAS[®] AmpliPrep/COBAS[®] TaqMan[®] HCV Test, v2.0. The lower limit of quantification (LLOQ) and the lower limit of detection (LLOD) is 15 IU/mL. HCV RNA results that are detectable but not quantifiable are reported as "< 15 IU/mL" and results that are not detectable are reported as "-NON-DETECTED."

Assessment of Clinical Outcomes

Incidence of the following clinical outcome events will be collected during the 12/24 weeks of treatment and the 5-year (PT Week 260) Post-Treatment Period. The data reported on the "Clinical Outcome" eCRFs will be adjudicated by an independent outcome committee and results of the adjudication will be added to the "Clinical Outcome" eCRFs:

- All-cause death: Death due to any cause.
- Liver-related death: Death as the result of a liver-related cause.
- Liver decompensation: Development of any of the following conditions: ascites, hepatic encephalopathy, or variceal bleeding.

- Liver transplantation: any subject who had a liver transplantation
- Hepatocellular carcinoma (HCC): development of HCC in any subject at any time during the study. HCC is defined by histologic confirmation or a > 1 cm mass lesion on cross-sectional imaging that meets the diagnostic criteria for HCC according to EASL guidelines.
- Composite of any of the above outcomes.

Definitions for HCV RNA Efficacy Endpoints

Note that a confirmed quantifiable post-treatment value is defined as two consecutive post-treatment HCV RNA measurements \geq LLOQ. During treatment, a confirmed quantifiable value is defined as any two consecutive HCV RNA values \geq LLOQ, either both during treatment or at the final treatment measurement and the next consecutive post-treatment measurement.

Breakthrough = confirmed HCV RNA \geq LLOQ after HCV RNA < LLOQ during treatment, or confirmed increase from nadir in HCV RNA (two consecutive HCV RNA measurements > 1 log₁₀ IU/mL above nadir) at any time point during treatment. A single breakthrough value (\geq LLOQ or > 1 log₁₀ IU/mL above nadir) followed by lost to follow-up will be considered a breakthrough (i.e., will not require confirmation).

On-treatment virologic failure = breakthrough or failure to suppress during treatment (all on-treatment values of HCV RNA \geq LLOQ) with at least 6 weeks (defined as study drug duration \geq 36 days) of treatment.

RVR (rapid virologic response) = HCV RNA < LLOQ in the Week 4 window.

EOTR (end of treatment response) = HCV RNA < LLOQ in the Week 12 window for subjects receiving 12 weeks of treatment and in the Week 24 window for subjects receiving 24 weeks of treatment.

SVR₄ = HCV RNA < LLOQ in the SVR₄ window (4 weeks after the last actual dose of study drug) without any confirmed quantifiable (\geq LLOQ) post-treatment value during that SVR window.

SVR₁₂ = HCV RNA < LLOQ in the SVR₁₂ window (12 weeks after the last actual dose of study drug) without any confirmed quantifiable (\geq LLOQ) post-treatment value before or during that SVR window.

SVR₂₄ = HCV RNA < LLOQ in the SVR₂₄ window (24 weeks after the last actual dose of study drug) without any confirmed quantifiable (\geq LLOQ) post-treatment value before or during that SVR window.

Relapse₁₂ = confirmed HCV RNA \geq LLOQ between end of treatment and 12 weeks after last actual dose of active study drug (up to and including the SVR₁₂ assessment time point) for a subject with HCV RNA < LLOQ at Final Treatment Visit who completes treatment.

Relapse₂₄ = confirmed HCV RNA \geq LLOQ during SVR₂₄ window among subjects who achieved SVR₁₂ and have data available during the SVR₂₄ window.

Relapse_{late} = confirmed HCV RNA \geq LLOQ at any time after the SVR₂₄ assessment time point for a subject who achieved SVR₂₄ and has post-SVR₂₄ HCV RNA data available.

Relapse_{overall} = confirmed HCV RNA \geq LLOQ between end of treatment and up to and including the last HCV RNA measurement collected in the PT Period for a subject with HCV RNA < LLOQ at Final Treatment Visit who completes treatment. Also, include a summary of **Relapse_{overall}** for subjects who prematurely discontinued treatment (< 77 days for subjects assigned to 12 weeks of treatment and < 154 days for subjects assigned to 24 weeks of treatment).

For relapse analyses, the completion of treatment is defined as a study drug duration \geq 77 days for subjects assigned to 12 weeks of treatment and \geq 154 days for subjects assigned to 24 weeks of treatment. If the last available post treatment value is \geq LLOQ,

then the subject will be considered a relapse (i.e., will not require confirmation). Relapse analyses will exclude subjects who do not have any post-treatment HCV RNA values.

Reasons for SVR₁₂ Non-Response

Subjects who do not achieve SVR₁₂ (SVR₁₂ non-responders) will be categorized as having:

1. On-treatment virologic failure (see **On-treatment virologic failure** definition);
2. Relapse (defined according to the **Relapse₁₂** definition for subjects who complete treatment);
3. Prematurely discontinued study drug with no on-treatment virologic failure (defined as any SVR₁₂ non-responder who prematurely discontinued study drug (duration < 77 days for subjects assigned to 12 weeks of treatment or duration < 154 days for subjects assigned to 24 weeks of treatment) and did not meet the **On-treatment virologic failure definition**);
4. Missing follow-up data in the SVR₁₂ window (defined as any subject who completed study drug without data in the SVR₁₂ window and not meeting the definitions of [1], [2], or [3]);
5. Other (defined as any SVR₁₂ non-responder not meeting the definitions of [1] – [4], such as a subject with a single quantifiable value within the SVR₁₂ window followed by an undetectable value beyond the SVR₁₂ window).

Reasons for SVR₂₄ Non-Response

Subjects who do not achieve SVR₂₄ (SVR₂₄ non-responders) will be categorized as having:

1. On-treatment virologic failure (see **On-treatment virologic failure** definition);
2. Relapse (defined according to the **Relapse₁₂** definition for subjects who complete treatment);

3. Relapsed after achieving SVR₁₂ (see **Relapse₂₄**);
4. Prematurely discontinued study drug with no on-treatment virologic failure (defined as any SVR₂₄ non-responder who prematurely discontinued study drug and did not meet the **On-treatment virologic failure, Relapse₁₂, or Relapse₂₄** definitions);
5. Missing follow-up data in the SVR₂₄ window (defined as any subject who completed study drug without data in the SVR₂₄ window, and not meeting the definitions of [1], [2], [3], or [4]);
6. Other (defined as any SVR₂₄ non-responder not meeting the definitions of [1] – [5]).

